9.2.6.2. Cohort 2: Treated comparator only cohorts

Pregnancies will be included in the Treated Comparator Only cohorts (Cohort 2) if they meet the following criteria:

- 1. Any of the following:
 - a. Administration of remdesivir in an outpatient setting between 9 days prior to ECD and the end of the exposure window.

OR

b. Administration of bebtelovimab in an outpatient setting between 60 days prior to ECD and the end of the exposure window.

AND

2. No dispensing of PAXLOVID (any setting) between 12 days prior to first eligible comparator drug dispensing and the end of the exposure window.

The 9-day pre-ECD window for remdesivir was chosen because of the 3-day recommended treatment course and 6 days to achieve 5x the clearance half-life (FDA 2022b). The 60-day pre-ECD window for bebtelovimab was chosen because of the 60-day requirement to achieve 5x the clearance half-life (FDA 2022c).

Pregnancies with exposure to more than 1 Cohort 2 medication (eg, a pregnancy exposed to both remdesivir and bebtelovimab, or other future approved or authorized COVID-19 therapies included in Cohort 2) will be eligible for inclusion.

Lists of approved or authorized COVID-19 therapies for the definition of the treated comparator will be periodically reviewed and updated in the SAP as necessary.

9.2.6.3. Cohort 3: Untreated comparator cohorts

Pregnancies will be included in the Untreated Comparator cohorts (Cohort 3) if they meet the following criteria:

1. At least 1 COVID-19 diagnosis (ICD-10 U07.1) in an outpatient, inpatient, or emergency room setting between 7 days prior to ECD and the end of the exposure window.

AND

- 2. No exposure to any authorized COVID-19 therapies, regardless of setting (ie, outpatient/inpatient). Authorized therapies used to exclude pregnancies from the unexposed cohorts include:
 - a. Study cohort drugs
 - b. Other approved or authorized treatments (eg, molnupiravir, other monoclonal antibodies)
 - c. Convalescent plasma (indicated for patients with immunosuppressive disease or receiving immunosuppressive treatment)

Lists of authorized COVID-19 therapies for the exclusion definition of the untreated comparator cohort will be periodically reviewed for completeness and updated in the SAP as necessary and will include all approved or authorized (EUA for the treatment of mild-to-moderate COVID-19) medications at any point during the study period. Medication-specific pre-ECD windows for exclusion for other monoclonal antibodies and convalescent plasma will be based on typical treatment durations and medication half-lives (as with other study cohort treatments) and defined in the SAP.

9.2.7. The index date for Cohort 3 will be the date of COVID-19 diagnosis plus the treatment interval (the median interval between COVID-19 diagnosis and treatment in Cohort 1; as defined in Section 4.3.3.1.1 in the SAP)Follow-up

For the assessment of pregnancy outcomes, follow-up for each pregnant woman will extend from the day following cohort entry (ECD) until the earliest of: disenrollment from the health plan, end of the pregnancy, or 01 September 2026.

For the assessment of infant outcomes, linked infants (the subset of pregnancies resulting in livebirths that are linked to the mother's data) will be followed from the date of delivery until the earliest of: disenrollment from the health plan or 1 year of age.

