9. RESEARCH METHODS

9.1. Study design

This 5-year observational cohort study will use administrative healthcare claims data (the ORD) to assess PAXLOVID exposure and pregnancy and infant outcomes including SA, induced termination, stillbirth, livebirth, SGA, preterm birth, postnatal growth deficiency, and infant developmental delay and MCM. The primary outcome is MCM, which will be confirmed via medical record review. Pregnancies that begin (based on the ECD, equal to LMP + 14 days) between 01 March 2021 and 01 December 2025 will be identified. For the assessment of infant outcomes, pregnancies that begin on or before 01 April 2025 will be eligible for inclusion. Pregnancies that began in March 2021 are the earliest eligible PAXLOVID-exposed pregnancies in the US (ie, potentially exposed to PAXLOVID close to delivery in December 2021).

All qualifying pregnancies per woman will be included in the study and classified according to the COVID-19 treatments received during 2 relevant exposure windows:

- First trimester exposure window
- Full pregnancy exposure window

These 2 windows provide the flexibility to assess the timing of exposure during pregnancy, as the relevant etiologic period may be the first trimester for MCM whereas the full pregnancy may be the relevant exposure period for pregnancy or other infant outcomes. Given that COVID-19 treatment is typically administered shortly after COVID-19 diagnosis, these exposure windows will account for timing of COVID-19 during pregnancy as well.

[figure not shown]
Based on received COVID-19 treatments during each of 2 exposure windows (first trimester, pregnancy), the pregnancies will be classified into the following exposure cohorts (for a total of 6 cohorts):

- Cohort 1 (PAXLOVID cohorts): at least 1 dispensing of PAXLOVID within the relevant exposure window, and no evidence of comparator medications within the relevant exposure window
- Cohort 2 (Treated Comparator Only cohorts): no evidence in the study database of a dispensing of PAXLOVID, and dispensing or administration of at least 1 of the following treatments indicated for the treatment of mild-to-moderate COVID-19 within the relevant exposure window:
 - Remdesivir
 - Bebtelovimab
- Cohort 3 (Untreated Comparator cohorts): no evidence in the study database of a dispensing or administration of any COVID-19 treatments within the relevant exposure window

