9.2.4. Identification of COVID-19 episodes

[figure not shown]
COVID-19 episodes will be identified through presence of the ICD-10 diagnosis code:

• U07.1 (COVID-19, virus identified [lab confirmed])

A recent paper found adequate validity when using ICD-10 diagnosis code U07.1 to identify hospitalized COVID-19 patients in 2020, with PPVs ranging from 70% to 93% in nationally insured patients (Kluberg et al. 2022).

Episodes of COVID-19 will be defined by clustering all COVID-19 diagnoses occurring within 14 days of one another, reflecting the upper range of the incubation period (WHO 2023). Because the duration of symptomatic COVID-19 is variable, a grace period of 14 days following the final COVID-19 diagnosis within a cluster will be added to conservatively capture the symptomatic duration of a single COVID-19 episode (Sudre et al. 2021) (Figure 3).

Figure 3. Example Pregnancy with Two Episodes of COVID-19

The frequency, duration and timing of COVID-19 episodes will be described. Eligibility for the overall study population will not be restricted based on the presence of COVID-19 during pregnancy or in proximity to COVID-19 treatments; rather, the frequency and characteristics of COVID-19 episodes will be summarized and described and may be used for subgroup analysis. COVID-19 episodes will be defined independently of any treatment(s) received for COVID-19; however, treatments received during COVID-19 episodes will be characterized with regard to the COVID-19 episode during which they occur (eg, time from COVID-19 diagnosis to treatment initiation, inpatient status at time of COVID-19 diagnosis, etc.; Section 9.3.3).

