9.3.3. Covariates

9.3.3.1. Time periods

[figure not shown]
The following dates and time periods will be used (Figure 4):

- Index date the date of start of treatment (Cohorts 1 and 2) or COVID-19 diagnosis plus the treatment interval (Cohort 3)
- Baseline the 6 months prior to ECD through the index date, with potential variability in capture of time prior to EDC according to timing of treatment and COVID-19 diagnosis as described below. As an example, each patient with the same timing of an index exposure (eg, treatment/COVID-19 at Day 60 of pregnancy) will have the same amount of baseline, but by anchoring to treatment/COVID-19, there is

potential for variability in the baseline window length according to the timing of treatment or COVID-19 infection.

- For individuals with index dates during pregnancy, the baseline period includes the ECD (Figure 4A)
- o For individuals index dates prior to ECD (eg, PAXLOVID initiation 2 days prior to ECD), the baseline period ends prior to ECD (Figure 4B)
 - For these pregnancies, select characteristics at ECD will still be captured (ie, maternal age at ECD, calendar year of ECD)
- All available pre-pregnancy data all available data from 01 January 2016 onward
- First trimester/pregnancy the time between ECD and end of first trimester/end of pregnancy

Figure 4. Time Periods for the Assessment of Covariates.

The baseline window will be defined using the first eligible treatment or COVID-19 diagnosis during an exposure window. Descriptive characteristics that capture the total number of COVID-19 therapies (eg, multiple courses of PAXLOVID) will be described during the first trimester/pregnancy window.

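### Cohort 3 entry and index date use the first U07.1 code in the exposure window rather than the start of a COVID-19 episode, so a repeat code can set the index mid-episode

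*Protocol*

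**What the plan says.** - **Entry (Protocol 9.2.6.3).** Cohort 3 needs "At least 1 COVID-19 diagnosis (ICD-10 U07.1) in an outpatient, inpatient, or emergency room setting between 7 days prior to ECD" (upper limit: the close of the exposure window), plus no authorized COVID-19 therapy. There is no condition that the code be the first of an infection, and no code-free period before it.
- **Index date (end of 9.2.6.3).** "The index date for Cohort 3 will be the date of COVID-19 diagnosis plus the treatment interval", the interval being the Cohort 1 median from diagnosis to treatment. Cohorts 1 and 2 are indexed on the start of treatment (9.3.3.1).
- **Which diagnosis (9.3.3.1).** "The baseline window will be defined using the first eligible treatment or COVID-19 diagnosis during an exposure window".
- **Episodes (9.2.4).** "Episodes of COVID-19 will be defined by clustering all COVID-19 diagnoses occurring within 14 days of one another", with "a grace period of 14 days following the final COVID-19 diagnosis within a cluster". The stated uses are description and possible subgroup analysis.
- **Reliance on the window (9.1).** "Given that COVID-19 treatment is typically administered shortly after COVID-19 diagnosis, these exposure windows will account for timing of COVID-19 during pregnancy as well".
- **Covariates (9.3.3.2.1).** Gestational age at the start of the episode, prior COVID-19, and the time between index date and ECD are all listed and considered for the propensity score (9.7.2.1). The time between first treatment or infection and ECD also defines a subgroup analysis (9.7.4.7).

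**The concern.** By chaining codes into episodes, the protocol recognises that one infection can produce several U07.1 codes over weeks. The Cohort 3 rules ignore that chain, so an infection first coded well before conception can qualify on a later code.

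Four things follow from the text:

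- The index date is too late by the gap between the first code of the episode and the first code in the window.
- The time from index to ECD inherits the error, both as a covariate and as a subgroup variable.
- Baseline runs through the index date, so a mid-episode index lets more of the illness course (for example supplemental oxygen or critical care) count as pre-index information.
- The primary objective is the risk in each cohort. The crude prevalence in Section 9.7.2.2 is unweighted, so carried-over infections stay in the Cohort 3 estimate whatever the propensity score does.

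The argument in Section 9.1 that the windows handle infection timing rests on treatment following diagnosis closely. Cohort 3 has no treatment date to which that argument could apply. Index timing matters in this design: an amendment moved the Cohort 3 index by the treatment interval because indexing on diagnosis could understate outcomes related to early pregnancy termination.

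**Working it through.** The protocol states no figure on this point, so there is none to reproduce. The check is a worked case followed by an illustration of size.

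**Worked case.** Take an untreated woman with codes at ECD−20, ECD−12 and ECD−2, and call the treatment interval m days.

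1. The gaps are 8 and 10 days, both within 14, so Section 9.2.4 makes this one episode starting at ECD−20.
2. The window opens at ECD−7. Only the ECD−2 code lies inside it, so the pregnancy enters Cohort 3 in both the first-trimester and the full-pregnancy windows.
3. The index as written is ECD−2+m. From the episode start it would be ECD−20+m. The difference is 20 − 2 = 18 days, whatever m is.
4. An episode-based index would fall in the window only if −20 + m ≥ −7, that is m ≥ 13 days. Section 9.1 expects treatment shortly after diagnosis.

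**Carry-over share.** Assume a constant infection rate. Let f be the share of infections with a repeat code, d the days from first to last code, and W the window length. Episodes starting in the window are proportional to W. Episodes starting earlier with a code in the window are proportional to f·d. The share is f·d / (W + f·d).

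Assumptions: W = 91 days for the first trimester (7 lead-in days plus 84) and 273 for full pregnancy (7 plus 266). f and d are in no document.

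| f | d | f·d | First trimester | Full pregnancy |
|---|---|---|---|---|
| 0.05 | 7 | 0.35 | 0.35/91.35 = 0.4% | 0.35/273.35 = 0.1% |
| 0.10 | 14 | 1.4 | 1.4/92.4 = 1.5% | 1.4/274.4 = 0.5% |
| 0.25 | 28 | 7 | 7/98 = 7.1% | 7/280 = 2.5% |
| 0.50 | 28 | 14 | 14/105 = 13.3% | 14/287 = 4.9% |
| 1.00 | 28 | 28 | 28/119 = 23.5% | 28/301 = 9.3% |

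The last row requires every infection to be recoded over 28 days and is an extreme.

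**Effect on the unweighted ratio.** Suppose, as an assumption only, that in-window COVID-19 raises the risk of major congenital malformation (MCM) 1.5-fold and a carried-over infection adds nothing. With carry-over share s, the prevalence ratio is inflated by 1.5/(1.5 − 0.5s): 2.4% at s = 7.1%, 4.6% at 13.3% and 8.5% at 23.5%. If early-pregnancy COVID-19 does not raise the risk, this inflation is nil.

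**The case against.** Several points on the other side stand.

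- **Gestational age at infection.** A reader might infer that the propensity score will carry a wrong gestational age at infection. The documents do not support that. The listed covariate refers to the start of the episode; in the worked case it takes the ECD−20 value, which is right. Only the separate index-to-ECD covariate is shifted.
- **Partial adjustment.** Episode-start age and prior COVID-19 can identify these pregnancies. If they enter the model, the weights for the average effect among the treated (9.7.2.1.1) would tend to down-weight untreated women infected long before ECD. This is incomplete: inclusion is only considered, the heading over the episode covariates ties them to cohort medication exposure where applicable, and neither entry nor index date changes.
- **Cohort 1 is not clean either.** Dispensing counts from ECD−7, so the diagnosis may be earlier, and none is required. In Table 3, 1,021 − 564 = 457 of 1,021 pregnancies with PAXLOVID (45%) had no COVID-19 code. A rule that the first code itself must fall in the window would therefore be stricter for Cohort 3 than for Cohort 1.
- **Deliberate design.** The 7-day lead-in is intended, and the protocol nowhere calls Cohort 3 a first-trimester infection cohort. The defect is limited to episodes that began before the lead-in.
- **Follow-up.** It starts the day after ECD (9.2.7), so a late index does not itself move the start of follow-up.

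The analysis plan is not a full answer. Section 9.2.6.3 defers to it for the interval, the drug lists and some drug-specific windows. The qualifying diagnosis and the anchor are fixed in the protocol.

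**Conclusion.** The point holds as a misdated index and a loose entry rule in Cohort 3. Followed as written, the protocol indexes some untreated pregnancies mid-episode and admits some infections that began more than 7 days before ECD. What is affected is the index date, the index-to-ECD covariate and subgroup variable, the end of baseline, and the crude Cohort 3 risk.

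The size cannot be settled from the protocol. Over f from 0.05 to 0.50 and d from 7 to 28 days, the carry-over share is 0.4% to 13% in the first-trimester window and 0.1% to 5% in the full-pregnancy window. It may well be small. A claim that about a quarter of the first-trimester comparator is contaminated would rest on the extreme row of the table. A claim that PAXLOVID is made to look worse holds only if early-pregnancy COVID-19 raises the outcome risk, which the protocol does not establish. The change is worth making because the rule is wrong as stated and easy to correct.

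**What to change.** In Sections 9.2.6.3 and 9.3.3.1:

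1. Set the Cohort 3 index date to the first U07.1 code of a Section 9.2.4 episode plus the treatment interval.
2. Require that index date, rather than any single code, to fall between 7 days before ECD and the end of the exposure window. This parallels the dispensing-date rule of Cohort 1 and still admits infections first coded up to one treatment interval before the lead-in. Carry-over from episodes with an earlier index then falls to zero by construction.
3. Apply the no-treatment criterion to the whole qualifying episode. Sections 9.1 and 9.2.6 limit it to the exposure window, while 9.2.6.3 gives no dates for the study drugs. On the narrower reading, a woman dispensed PAXLOVID at ECD−10 and recoded at ECD−2 could count as untreated.

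The cost is a few sentences, since episodes are already to be constructed, and a small loss from a large cohort. Table 3 counts 35,303 pregnancies with a COVID-19 code, before eligibility criteria and removal of treated women.

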9.2.5. Exposure windows

From the base population, qualifying pregnancies will be classified according to the COVID-19 treatment received during the following relevant exposure windows:

- First trimester exposure window
 - o Start date: ECD therapy-specific window
 - o End date: End of the first trimester

• Pregnancy exposure window

o Start date: ECD – therapy-specific window

End date: End of the pregnancy

As different COVID-19 therapies will have varying rates of elimination, the length of each relevant exposure window will be extended (prior to the ECD) by a corresponding therapy-specific window, based on the indicated treatment duration (plus a grace period for self-administered drugs) and the time to non-detectable concentration in the body (defined as 5x the clearance half-life). This ensures the capture of exposure to COVID-19 therapies administered or dispensed prior to the ECD but which remain in the body at ECD. Sections 9.2.6.1 and 9.2.6.2 describe the therapy-specific windows for each of the study therapies.

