9.2.6.1. Cohort 1: PAXLOVID cohorts

Pregnancies will be included in the PAXLOVID cohorts (Cohort 1) if they meet the following criteria:

1. Dispensing of outpatient PAXLOVID between 7 days prior to ECD and the end of the exposure window.

AND

- 2. None of the following:
 - a. Administration of remdesivir between 9 days prior to ECD and the end of the exposure window.

OR

b. Administration of bebtelovimab between 60 days prior to ECD and the end of the exposure window.

The 7-day pre-ECD window for PAXLOVID was chosen because of the 5-day recommended treatment course, plus 2 days to achieve 5x the clearance half-life. See Section 9.2.6.2 for justification for other pre-ECD windows.

Because the precise indication for PAXLOVID ("mild-to-moderate COVID-19") cannot be directly captured in claims data, and to improve comparability with comparator pregnancies, only PAXLOVID dispensings occurring in an outpatient setting will be eligible for inclusion.

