Additionally, neither information on COVID-19 severity nor reasons for the test that determine the COVID-19 diagnosis are directly available in administrative claims data. Proxy measures for COVID-19 severity (eg, critical care services) have been added to the list of covariates (Section 9.3.3). Options for other proxies of severity and reason for diagnosis will continue to be explored; for example, co-occurrence of diagnoses on days with select other procedures (eg, diagnoses occurring on days with procedure codes for standard prenatal visits) or site of diagnosis may serve as proxies for the reason of diagnosis.

Using ICD-10 Z3A codes to estimate the LMP date (and, subsequently, ECD) is expected to be accurate but, when Z3A codes are not present, using existing algorithms to estimate LMP (that are based on the presence of pregnancy outcomes) is expected to introduce a greater degree of measurement error for early pregnancy outcomes such as SA and induced termination. In addition, given the inexact estimation of LMP, classification of trimesters and the corresponding medication exposure could be inaccurate, with such non-differential misclassification of a binary exposure likely biasing study results toward the null.

In this study, the numbers of some pregnancy and infant outcomes are expected to be low. As the number of variables for inclusion in regression models is dependent on the number of study outcomes, the standard approach to controlling for confounding through regression modelling of the outcomes will yield estimates that are only adjusted for a small number of potential confounders. In contrast, propensity score modelling and IPTW allows for the inclusion of dozens of potential confounders and risk factors, resulting in greater validity of the estimates than what may be derived from regression modelling alone. While it is true that operationally, the IPTW analysis controls for variables that are included in the model and may not fully control for bias due to unknown confounders, it has been shown that, similar to randomization within clinical trials, propensity score modelling and adjustment often controls for confounding due to variables that are not explicitly included in the propensity score model through the inclusion of variables that are proxies for the non-included variables (Guertin et al. 2016).

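### Cohort 3 entry can be triggered by the encounter that ends the pregnancy, and its index date can fall after the outcome

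*Protocol*

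**What the plan says.** - **Entry to Cohort 3 (Section 9.2.6.3).** At least one U07.1 code "in an outpatient, inpatient, or emergency room setting between 7 days prior to ECD and the end of the exposure window", with no authorized COVID-19 therapy in any setting.
- **Window ends (Section 9.2.5).** Full-pregnancy window: "End date: End of the pregnancy". First-trimester window: "End date: End of the first trimester".
- **Index date (head of Section 9.2.7, and Section 9.3.3.1).** "The index date for Cohort 3 will be the date of COVID-19 diagnosis plus the treatment interval". The interval is the Cohort 1 median time from diagnosis to treatment, and its definition is left to the SAP.
- **Follow-up for pregnancy outcomes (Section 9.2.7).** It starts the day after ECD, not at the index date.
- **Baseline (Sections 9.3.3.1 and 9.3.3.2.1).** It runs from six months before ECD through the index date. It covers hospitalizations and emergency visits, including those during pregnancy, as well as oxygen and critical care indicators.
- **Cohorts 1 and 2 (Sections 9.2.6.1 and 9.2.6.2).** These restrict the setting of treatment: "only PAXLOVID dispensings occurring in an outpatient setting will be eligible for inclusion" for Cohort 1 and, for example, "Administration of remdesivir in an outpatient setting between 9 days prior to ECD and the end of the exposure window" for Cohort 2.
- **Limitation acknowledged (Section 9.9).** "neither information on COVID-19 severity nor reasons for the test that determine the COVID-19 diagnosis are directly available in administrative claims data".

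**The concern.** The qualifying diagnosis should precede the outcome and arise independently of it. Under Section 9.2.6.3 it need not. A woman who is tested because she presents with a miscarriage, a fetal death or in labour, and who has no earlier COVID-19 code in the window, enters Cohort 3 because of the encounter at which the outcome is recorded. Nothing in the protocol excludes that code or requires the pregnancy to be ongoing at the index date.

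Two estimates are at stake. One is the set of Cohort 3 risks, which answer the estimation objectives and which Section 9.9 values as a background rate. The other is the set of Cohort 1 versus Cohort 3 ratios. Adjustment is exposed as well: if the index date is on or after the pregnancy-ending encounter, that encounter falls in the baseline period, although Section 9.3.3.2 reserves the propensity score for pre-treatment covariates.

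**Working it through.** **Timing.** Let D be the diagnosis date, m the treatment interval and E the end of pregnancy. Entry requires D ≤ E in the full-pregnancy window, and index = D + m. The protocol gives no value for m.

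- With D = E and m = 0, index falls on the day of the outcome.
- With D = E and m > 0, index falls after the outcome. The same holds for any D later than E − m.
- Follow-up starts the day after ECD whatever the index date, so moving the index date forward removes nobody.
- In Cohort 1 the index date is the treatment date, which must itself lie in the window. It cannot fall after E.

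**Which windows and outcomes.** In the full-pregnancy window both delivery and loss encounters can qualify. In the first-trimester window a delivery admission cannot, but an early loss encounter can, so SA is exposed there too. Malformations are counted among linked livebirths (Section 9.7.2.2), so losses leave that denominator.

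**Size.** The protocol states no figure for this effect, so there is none to reproduce. Inputs:

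- p, the reference risk, from Section 9.5: SA 14%, stillbirth 1% (the Table 1 value), preterm birth 10%.
- s, the share of Cohort 3 (for preterm birth, of its linked livebirths) that enters only through a code at the pregnancy-ending encounter. Assumed.
- q, the share of those entrants with the adverse outcome in question. Assumed.

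If all other Cohort 3 pregnancies have risk p:

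- Cohort 3 observed risk = (1 − s)p + sq
- Ratio read when the true ratio is R = Rp / [(1 − s)p + sq]

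For SA with s = 5%:

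- q = 0: 0.95 × 0.14 = 0.133, and 0.14/0.133 = 1.05
- q = 1: 0.133 + 0.05 = 0.183, and 0.14/0.183 = 0.77

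| Outcome (p) | s | q | Cohort 3 risk | True 1.0 reads | True 2.0 reads |
|---|---|---|---|---|---|
| SA (14%) | 5% | 0 | 13.3% | 1.05 | 2.11 |
| SA | 5% | 0.14 | 14.0% | 1.00 | 2.00 |
| SA | 5% | 0.5 | 15.8% | 0.89 | 1.77 |
| SA | 5% | 1 | 18.3% | 0.77 | 1.53 |
| SA | 10% | 0 | 12.6% | 1.11 | 2.22 |
| SA | 10% | 1 | 22.6% | 0.62 | 1.24 |
| Stillbirth (1%) | 5% | 0 | 0.95% | 1.05 | 2.11 |
| Stillbirth | 5% | 0.25 | 2.2% | 0.45 | 0.91 |
| Preterm (10%) | 5% | 0 | 9.5% | 1.05 | 2.11 |
| Preterm | 5% | 0.5 | 12.0% | 0.83 | 1.67 |

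The sign turns at q = p. Entrants at livebirth deliveries have q = 0 for SA and stillbirth and pull those risks down; entrants at loss encounters push them up. The rows are separate scenarios: one group of entrants cannot all be SA and all be stillbirth.

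**The case against.** **Inpatient diagnoses fit the stated population. This stands.** The objective in Section 8 covers untreated pregnant women with COVID-19 and sets no severity limit, and Section 9.9 describes Cohort 3 as the background among diagnosed women. A reader might infer that Cohort 3 must be outpatient because Cohorts 1 and 2 are. The documents do not support that: the outpatient rule there governs treatment, not diagnosis, and Cohort 1 needs no COVID-19 code. In Table 3, 564 of 1,021 PAXLOVID pregnancies (55%) had one. An outpatient-only diagnosis rule for Cohort 3 alone would create a different asymmetry. It would also miss losses coded at outpatient or emergency visits.

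**Severity and setting are partly handled. This stands in part.** Site of diagnosis, oxygen, critical care and index-to-ECD duration are listed covariates. Under the ATT weight e/(1 − e), Cohort 3 pregnancies unlike PAXLOVID users (e near 0) get little weight. Analyses by hospitalization status are planned, and Section 9.9 considers proxies for the reason for testing. But the covariates are only candidates and LASSO may drop them (Section 9.7.2.1), the hospitalization subgroup depends on sample size, and none of these marks a diagnosis made at the outcome encounter. The crude cohort risks receive no weighting.

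**The SAP may deal with it.** The treatment interval is deferred to the SAP, which was not available here, and a rule for index dates after pregnancy end could be there. The entry criterion, however, is fixed in the protocol and as written admits these codes.

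**Conclusion.** The point holds as a defect in how Cohort 3 entry is timed. Outcome-encounter codes qualify, the index date can follow the outcome, and the outcome encounter can enter baseline. The pregnancy outcomes and preterm birth in the full-pregnancy window are mainly affected, with SA also exposed in the first-trimester window.

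The size is conditional on s and q, which the protocol does not give. At an assumed s = 5%, a true SA ratio of 1.0 reads between 1.05 and 0.77, and a true 2.0 between 2.11 and 1.53. These figures assume that the remaining Cohort 3 pregnancies carry the Section 9.5 reference risks and that Cohort 1 is unaffected.

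Two stronger conclusions are not supported. A reader might infer that Cohort 3 risks are inflated and harm is masked; that requires q to exceed p (14% for SA, 1% for stillbirth, 10% for preterm birth), and the documents give no split between delivery and loss entrants. A reader might also infer that the primary outcome is compromised. For first-trimester exposure, the window Section 9.5 uses for malformations, delivery admissions are outside the window and losses are outside the linked-livebirth denominator, so that analysis is largely unaffected.

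**What to change.** In Section 9.2.6.3:

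1. Require the pregnancy to be ongoing at the Cohort 3 index date. This matches what the window already ensures in Cohort 1, where index cannot fall after the pregnancy has ended.
2. Exclude U07.1 codes first recorded at the encounter or admission at which the pregnancy ends, whatever its setting.
3. Report the number removed, by exposure window, in the attrition flow chart. This also supplies the share that is unknown now.
4. Otherwise keep the all-settings definition, and add a sensitivity analysis restricting Cohort 3 to outpatient diagnoses or emergency visits not leading to admission. As the main definition, that restriction would narrow the stated objective.

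The cost is a short protocol change and a claims filter. Cohort 3 becomes somewhat smaller, but Section 9.7.2.1.1 already allows for sampling it down to at most five comparators per PAXLOVID-exposed pregnancy.
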